# D. Psychotherapist support for pharmacy staff

The wellbeing of the service users and the pharmacy staff will form an important part of the evaluation of feasibility. The core research team (JS, AL and appointed researcher) will be in regular contact with staff during the implementation phase and be available to respond to queries that may need to be made in light of any ethical issues that arise.

All pharmacy staff recruited to the study, will be informed at the beginning and throughout the feasibility study that they have access to an online mentoring session with a trained clinical psychotherapist to debrief on any distressful events that may have been encountered or any ethical issues that have arisen. All pharmacy staff will be reminded of this during the monthly supervisory follow up support visits from the researcher. We will
ensure pharmacy staff are aware that the psychotherapist is not part of the research team / evaluation team and that she can be accessed anonymously should they wish to do so.

# Public views

# 2. Participation in customer interviews

Regular customer users of the pharmacy will be invited to a one-to-one interview. It will be explained that the participation is entirely voluntary, not talking part will not affect their usual care and they can withdraw at any time.

These customers will be deemed well, are considered 'appropriate' and are not likely to become upset if invited to participate in the research. This 'appropriateness' will be determined by their usual care team who will know the customer well. The aim of these interviews is to establish the views of customers on any effect the intervention may have had on the routine pharmacy services, and customer acceptability towards the new service.

# 3. Public Questionnaires

This brief and optional e-survey will seek to measure general awareness of the service in the wider community and attitudes towards acceptability and accessibility. Participating in the questionnaire may present a minor inconvenience but has minimal physical risks or burden. Participants will be informed in the information sheet that participation is voluntary and they can choose not to answer any question.

There will also be contact details of self-help support services at the end of the questionnaire should these be needed. Return of the questionnaire will imply consent.

#### Personal information / data confidentiality

We will ensure that participants' identifiable details are stored securely at the University of Lincoln. Transcriptions of qualitative recordings and verbatim quotes will be anonymised to prevent participants being identified. We will abide by the Data Protection Act and the NHS Code of Confidentiality.

Source documents will be archived as per protocol at the University of Lincoln. Only study staff will have access to study documentation other than the regulatory requirements. In compliance with the GCP and University guidelines, the CI will maintain all records and documents. These will be retained for at least 7 years, archived at secure archive facilities at the University of Lincoln.

# Inclusivity

This study will seek to be as inclusive as possible. We are guided by our PPPIE Panel who have advised using an appreciative approach, where all participant views are valued, throughout. The CI will work closely with [name] who is the PPIE representative and co-applicant for the study.

We have costed for information sheets to be made available in a range of different languages. Translator costs have also been included for the customer interviews.

Mandatory text: Individual participant medical information obtained as a result of this study are considered confidential and disclosure to third parties is prohibited with the exceptions noted. Medical information may be given to the participant's medical team and all appropriate medical personnel responsible for the participant's welfare.

If information is disclosed during the study that could pose a risk of harm to the participant or others, the researcher will discuss this with the CI and where appropriate report accordingly.

#### ADVERSE EVENTS

A risk assessment has been conducted for this intervention, and risks for the intervention will continue to be considered and discussed during the co-development. There are two sets of main risks. The first is potential risks to clients accessing the service. Because they may be in a vulnerable and distressed

#### Page 37 of 50

situation, we must ensure that the intervention does not add to their distress or vulnerability. The protocol for conducting the intervention (from the point of client entry into the pharmacy, through the consultation, and then back out of the pharmacy) will take into account discretion, confidentiality, compassion and sensitivity. Similarly, the triage and development tool, and the staff training package will be designed to protect the clients from any harm. The second set of risks is the risk of harm to pharmacy staff from delivering the intervention. This may include them becoming upset themselves, being stressed by having increased demands on top of their routine work and the potential for feeling intimidated or under threat in the consultation room. To safeguard against these risks, we will include all aspects of safety and wellbeing in the training, we have incorporated the psychotherapist debriefing sessions and consultation rooms will be checked to ensure they have a panic alarm. We note that pharmacy staff are currently expected to manage patients in distress and have very little training or resources for this purpose. By developing this intervention, we aim to make these types of interactions safer (and more effective) for both patients/customers and pharmacy staff.

With regards to the rest of the research study (focus groups, workshops, interviews and survey) the risks are more minimal. We will ensure that there is always an extra facilitator at public/lay focus groups and workshops so that a facilitator can spend time with a participant individually should they become upset.

# ETHICS REVIEW AND COMPLIANCE

The study shall not commence until the study protocol, information sheets and consent forms have been reviewed and approved from a Research Ethics Committee and relevant NHS/Social Care permission is obtained

The sponsor will be responsible for deciding whether amendments are substantial and non-substantial in collaboration with the Chief Investigator.

Where an amendment is required to study documentation that required REC approval, changes will not be implemented until REC approval and HRA categorisation is received. Where an amendment requires local approval, this shall be sought prior to the amendment be implemented at each site in accordance with the categorisation given on the HRA approval letter.

Should an amendment be required to eliminate an apparent immediate hazard to participants this may be implemented immediately and the REC/HRA and R&D will be notified as soon as possible.

Minor amendments for logistical or administrative purposes may be implemented immediately

Amendments will be logged on the Sponsor's Study Amendment Log and stored in the Trial Master/Site File(s).

Annual Progress Reports shall be submitted to the REC within 30 days of the anniversary date on which the favourable opinion was given – until the end of the study.

A final report shall (where possible) be submitted to the REC within one year after the end of the study.

If the study is terminated prematurely the CI will notify the REC, including the reasons for premature termination.

#### PEER REVIEW

The project has received external peer reviewed and has received funding by the NIHR (HS&DR).

#### **PUBLIC & PATIENT INVOLVEMENT**

The research proposal has been developed with extensive patient and public involvement and engagement (PPIE). The project has a PPIE advisory and oversight steering group. Both advisory groups will meet to

Page 38 of 50

ensure the project is conducted sensitively, with a people-centred approach and ensure rigorous external review.

# Initial involvement:

The initial idea for this project emerged from [name]'s previous safeguarding study consisting of 10 focus groups with the public and professionals. All groups requested a drop-in service, in an everyday environment, for people to access to get advice and advocacy for domestic abuse. Members of the public did not feel that they could contact the major services alone. After the study, a total of 38 participants from this study were approached (in 2015 / 2017) to discuss an "in-between" service for domestic abuse. [name] also met with 6 members of Lincolnshire Recovery College in August 2019 where they spoke about pharmacists as approachable intermediaries for people living with mental health conditions.

In 2020-21 we consulted with 11 individual members of the public (6 females and 5 males, early 20s - 70s), with BAME and LGBT representation. 6 of the people had experienced suicidal feelings or domestic abuse.

We have also consulted with: Women's Aid, Samaritans, Mental Health Trust, a GP in the Crisis Team, a community researcher, 4 individual pharmacists, 2 psychotherapists and an Approved Mental Health Worker, in addition to giving presentations at the Lincolnshire Suicide Prevention Steering Group (contains local NHS Trusts, Uni/colleges, Police, Transport Police, Highways Agency, Voluntary sector, Public Health) and the Local Pharmaceutical Committee (Boots, Well Pharmacy, Co-op Pharmacy and independents). JS met with the Home Office to discuss complementary approaches with Ask for ANI.

# Key findings from PPIE engagement:

Views on pharmacy setting were positive as pharmacy staff are trusted professionals. Pharmacies can offer a discreet service (one can go into pharmacies for a range of reasons). Few barriers (i.e. no 'GP type receptionists'). Can walk into any pharmacy and can make excuse to partner to go alone (i.e. purchases of feminine hygiene products).

The link between abuse and suicide was noted, particularly if divorce is culturally unacceptable. It was recommended therefore that the service should cover both domestic violence and suicidal ideation.

The proposed name of "Lifeguard" with a life-ring symbol had an overwhelmingly positive response and was deemed to be wholly appropriate. Suggestions on how the service would work in practice were also made including having a card to hand in at the chemist counter to act as a 'nudge'.

Possible barriers were also detailed including pharmacists' skills, the ad hoc nature may mean other customers would having to wait, and if children were brought to the pharmacy.

Engagement with support organisations / professionals was positive and their views have influenced the service design (i.e. development of the triage, referral resources and mentoring for pharmacy staff). A representative from Women's Aid was disappointed in the "Safe Spaces" scheme saying that it was a good idea, but that scheme did not seem well implemented. Our project will specifically look at implementation / feasibility issues so the final service can be implemented effectively.

# Planned on-going involvement:

The input from patients / service users and the public will remain central throughout the study and will continue through 4 main routes.

- Firstly, members of the public are directly involved as participants in the lay focus groups, coproduction workshops, the customer interviews and survey.
- Secondly, we have established a PPI panel which will meet regularly during the study.
- Thirdly [name] is our PPI lead and co-applicant. As a co-applicant, he will be regularly involved with all aspects of the study. We will use his lay expertise to ensure public facing materials and study

information are accessible. [name] is registered blind and from a BAME background. His input throughout the study will enhance the study's inclusivity and diversity.

• Fourthly, we will establish a database and mailing list of people and organisations with an interest in the project. They will receive regular updates and will be invited to give comments, ideas and feedback.

The engagement with the public will be accompanied by continued and extended engagement with professionals and relevant organisations. There are three main routes for this engagement.

- Firstly, as participants in the study in the scoping interviews, and for pharmacy staff as direct participants in coproduction, being trained and implementing the intervention, in the staff interviews and in the final workshop.
- Secondly, there will be continued regular contact with the LPC, the Suicide Prevention Committee and other relevant organisations.
- Thirdly, via the same database and mailing list of interested parties, professionals will be included and asked for feedback. [name] will continue the dialogue with the Home Office about developments with Ask for ANI and has been invited to be a member of their advisory group.

# PROTOCOL COMPLIANCE

This study will be conducted in accordance with this protocol. Accidental protocol deviations may occur at any time. Accidental protocol deviations will be adequately documented on the relevant forms and reported to the Chief Investigator and Sponsor immediately.

# DATA PROTECTION AND PATIENT CONFIDENTIALITY

All study staff and investigators will comply with the principles of the Data Protection Act (2018) in protecting the rights of study participants with regards to the collection, storage, processing and disclosure of personal information and will uphold the Act's/Regulations core principles.

Each participant will be assigned a study identity number, for use on CRFs other trial documents and the electronic database.

Personal data, research data and the linking code will be stored in separate locations. When stored electronically, this will include using encrypted digital files within password protected folders and storage media. Personal information shall be stored separately to research data and will be kept secure, and maintained.

Personal data will be stored for 12 months following the end of the study, so that the Chief Investigator may provide participants with a summary of the research (should they wish to receive a copy).

Data generated as a result of this study will be available for inspection on request by the participating physicians, the University of Lincoln representatives, the REC, local R&D Departments and the regulatory authorities.

#### INDEMNITY

Insurance and indemnity for trial participants and trial staff is covered within the NHS Indemnity Arrangements for clinical negligence claims in the NHS, issued under cover of HSG (96)48. There are no special compensation arrangements, but trial participants may have recourse through the NHS complaints procedures.

The University of Lincoln as research Sponsor indemnifies its staff, research participants and research protocols with both public liability insurance and clinical trials insurance.

#### ACCESS TO THE FINAL DATASET

The Chief Investigator (JS) and Co-lead (AL) will have access to the final dataset. The dataset will be fully anonymised and uploaded anonymously to the University's repository.

# **DISSEMINATION POLICY**

The data custodian will be the Chief Investigator on behalf of the University of Lincoln. The findings will be disseminated in peer reviewed scientific journals, internal report, conference presentations, publication on website and other publications.

#### Authorship eligibility guidelines and any intended use of professional writers

We will be guided by the International Committee of Medical Journal Editors (ICMJE) who have defined authorship criteria for manuscripts submitted for publication. The ICMJE recommends that authorship be based on the following 4 criteria:

- Substantial contributions to the conception or design of the work; or the acquisition, analysis, or interpretation of data for the work; AND
- Drafting the work or revising it critically for important intellectual content; AND
- Final approval of the version to be published; AND
- Agreement to be accountable for all aspects of the work in ensuring that questions related to the accuracy or integrity of any part of the work are appropriately investigated and resolved.

	HRA REC Scoping interviews with referral organisations and setting up referral pathways	Recruitment for scoping interviews and subsequent engagement	Successful engagement with all major local referral organisations for both issues	Engagement with some but not all of major local referral organisations for both issues	opinion Failure to engage with at least one appropriate referral organisation for each issue	
	Views of intervention from participants in lay focus groups and co- production workshops	Lay focus groups and co-production workshops	Favourable view towards intervention from all participants in lay focus groups and co-production workshops	Mixed views as to suitability of the intervention	Majority view not in support of the intervention	
	Development of all aspects of the intervention	Co-production workshops and modelling	Successful development of all 7 aspects of the intervention	Partial failure to develop any one aspect of the intervention	Failure to develop any one aspect of the intervention	
5	Recruitment of pharmacies (control and intervention) across rural/urban, small pharmacy / commercial store	Recruitment of pharmacies	Recruitment of 3 pharmacies per category: a. urban/large commercial b. urban/small pharmacy c. rural/large commercial d. rural/small pharmacy	Failure to recruit at least one pharmacy for any of these categories	Failure to recruit any pharmacies	
	Randomisation procedures - are pharmacies willing to be allocated to the control group	Randomisation	All 12 agree to be randomised	At least one pharmacy was not willing or able to be randomised	None of them were willing or able to be randomised	
,	Recruitment of staff within pharmacies (3 per pharmacy, of whom one should be a pharmacist)	Staff recruitment	Recruitment of at least 2 per pharmacy	Recruitment of 1 per pharmacy	None recruited	
3	Ability to deliver training to all staff (2 sessions, 24 staff)		All 24 intervention staff attended and training delivered	Staff from half of the pharmacies attended training	Failure to train anyone in a particular pharmacy	
9	Assessment of change in behavioral intention after training – CPD Reaction Questionnaire	CPD Questionnaire and feedback	All staff completed the questionnaire with positive indication of feeling adequately trained to undertake the intervention	50% completed, and or results show 50% of staff do not feel adequately trained to undertake the intervention	0% completed and / or all staff feel unprepared	

18	Number and details of consultations per pharmacy (date, time, alone or with other and who, time taken, member of staff, if client had attended before)	Data sheets in pharmacies	Staff able to complete all details for all clients	Failure to record at least 50% of the data for at least 50% of the clients	Failure of the pharmacy staff to record any data on the intervention	
19	Other services accessed by client in last 3 months	Data sheets in pharmacies	Staff able to complete at least 80% of the data for at least 80% of the clients	Failure to record at least 30% of the data for at least 30% of the clients	Failure to capture any data	
20	Issue and level of severity (from triage grid) – to give overall number of consultations per box of triage grid - data collected in consultation	Data sheets in pharmacies	Staff able to complete all details for all clients	Failure to record at least 50% of the data for at least 50% of the clients	Failure of the pharmacy staff to record any data on the intervention	
21	Outcome from consultation – advice / self-management, signposted to another service, direct referral made, and to which organisations	Data sheets in pharmacies	Staff able to complete all details for all clients	Staff able to complete at least 80% of the data for at least 80% of the clients	Failure to record at least 50% of the data for at least 50% of the clients	

22	Reasons for accessing this service (based on 4 access barriers of capacity, psychological burden, timing, level of severity) – drop-in, convenient location, familiar environment, in person, familiar staff, everyday setting etc data collected in consultation	Data sheets in pharmacies	Staff able to complete at least 80% of the data for at least 80% of the clients	Failure to record at least 50% of the data for at least 50% of the clients	Failure to record at least 30% of the data for at least 30% of the clients	
23	Opportunistic or planned access by client - data collected in consultation	Data sheets in pharmacies	Staff able to complete at least 80% of the data for at least 80% of the clients	Failure to record at least 50% of the data for at least 50% of the clients	Failure to record at least 30% of the data for at least 30% of the clients	
24	Client basic demographic data collected in consultation	Data sheets in pharmacies	Staff able to complete at least 80% of the data for at least 80% of the clients	Failure to record at least 50% of the data for at least 50% of the clients	Failure to record at least 30% of the data for at least 30% of the clients	
25	Willingness to be followed up	Data sheets in pharmacies	Staff able to complete at least 80% of the data for at least 80% of the clients	Failure to record at least 50% of the data for at least 50% of the clients	Failure to record at least 30% of the data for at least 30% of the clients	
26	Pharmacy business data - prescription and service items. These data will be collected at the beginning of the study retrospectively for the 6 months prior, and during the 6 months of the implementation (for both control and intervention)	Pharmacy companies	Able to collect at least 90% of the data from 90% of the intervention pharmacies		Failure to collect at least 50% of the data from 50% of the intervention pharmacies, or an indication from this data that the intervention is having a deleterious effect on the business and staff wellbeing in any one of the pharmacies.	
27	Control pharmacies – number of queries for SI or DA, and if any Ask for ANI / safe space requests	Pharmacy companies	Able to collect at least 80% of the data from all 4 intervention pharmacies		Failure to collect 50% of the data from any one of the intervention pharmacies	
28	Community survey responses	Community survey	Completion of 600 full responses to community survey within the time period	Completion of 400 full responses to community survey within the time period	Completion of 300 or less full responses to community survey within the time period	
29	Acceptability and effectiveness of training using the Theoretical Framework for Acceptability of Healthcare Interventions – in staff focus groups	Staff focus Groups	All staff reporting that the training and ongoing support had sufficiently prepared them for completed the undertaking the intervention	Four or more staff reporting that the training and ongoing support had not sufficiently prepared them for completed the undertaking the intervention	Half or more of all staff (12/24) reporting that the training and ongoing support had not sufficiently prepared them for completed the undertaking the intervention	
30	Acceptability and effectiveness of intervention using the Theoretical Framework for Acceptability of Healthcare Interventions - in staff focus groups	Staff focus groups	All staff reporting that the intervention was mostly acceptability (only minor issues unacceptable and these could be fixed)	Four or more staff reporting major areas of unacceptability, or many staff reporting numerous minor issues that need to be addressed before proceeding	Half or more staff reporting that the intervention is unacceptable in one or more major, fundamental ways	

Page 47 of 50

31	Acceptability of the intervention from a customer perspective – interviews	Customer interviews	80% or more of customers reporting positive views about acceptability of the intervention from the perspective of a customer accessing the normal pharmacy services.	50% or more of customers reporting positive views about acceptability of the intervention from the perspective of a customer accessing the normal pharmacy services.	30% or more of customers reporting positive views about acceptability of the intervention from the perspective of a customer accessing the normal pharmacy services.	
32	Feasibility of each of the components of the intervention and as a whole - Consideration will be given to: any unintended or adverse consequences, the degree of local adaptation that would be required, who would deliver the training, who would deliver the mentoring, factors that facilitate/hinder the intervention, and its overall benefits and limitations of the intervention.	Feasibility workshop	Overall favourable opinion from all participants at the feasibility workshop (with due consideration of all feasibility data presented at the workshop), or reporting of only minor issues that could be fixed	One quarter or more of participants reporting major areas of unacceptability, or many participants reporting numerous minor issues that need to be addressed before proceeding, at the feasibility workshop (with due consideration of all feasibility data presented at the workshop)	One half or more of participants reporting that the intervention is unacceptable in one or more major, fundamental ways, at the feasibility workshop (with due consideration of all feasibility data presented at the workshop)	
33	Effectiveness of dissemination and promotion of intervention		70% of more or customer survey respondents aware of the service (intervention)	50% of more or customer survey respondents aware of the service (intervention)	30% of more or customer survey respondents aware of the service (intervention)	
34	Final consideration of the feasibility of the actual intervention. Are all the components of the intervention feasible and needed? Are there any other components that should be added?	Consideration of: 2,3,4,9,10,11,12, 14,15,16,17,18, 20,21,30,32, 33 &34 By research team, PPI panel and CTU				
35	Feasibility of a future trial – Is a trial possible?	Consideration of: 1,5,6,7,8,10,11,12, 14,15,16,17,18,19, 20,21,22,23,24,25, 26,27,28,29,30,31, 32 & 34 and questions in 35 Research team and CTU				
	What will be primary and secondary outcomes in a future cluster RCT? What are the feasible differences in primary outcome between the intervention and control groups, and the estimated intraclass correlation? Would stratification be required in the trial (type of pharmacy,					

Page 48 of 50

urban/rural location,			
socioeconomics of area,			
ethnic diversity of			
area)?			
Should sub-groups be			
considered? Is it			
feasible to randomise?			
Is it feasible to recruit			
controls?			
Power calculation and			
sample size required,			
for whole sample and			
any sub-groups.			
Possible sources of			
contamination, for			
example staff moving			
between pharmacies.			
How data would be			
analysed?			
Can quality of life,			
acceptability and			
satisfaction, and other			
health economic criteria			
be measured?			
What would be the			
requirements for future			
funding?			
	1		

 \*It is expected that should a criteria be recorded as red, this will be reviewed by the study team and adjustments made accordingly to any future design.

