# a. Usage and referral data

The rationale for this intervention is to lower access barriers. The primary area of interest is therefore the number of consultations, severity of danger and number of referrals made as a consequence of the consultation. Other measures we will explore include the reasons why the client chose the service, whether the client was considering or had accessed other services in the last 3 months,

The member of staff conducting the consultation will record the date, time, length of consultation, job role of staff member and the category of issue. Following triage, the informed consent will be received from the client. Data to be collected will include asking the client what services he/she has accessed in the last 3 months, and whether he/she has accessed this service previously. The client will then be asked some simple questions about reasons for choosing this service based on the four access barriers (capacity, psychological burden, timing and level of severity), for example: no appointment needed, convenient location, everyday environment, identified with the name and logo, convenient timing, familiar environment, familiar staff, whether their visit was opportunistic or planned, and basic demographic data.

Brief acceptability data will also be collected along with basic demographic details plus an indication of whether (for a future trial) completing a questionnaire and having a follow-up contact would be acceptable or not.

Staff will be trained to respond ethically in all cases of acute and severe distress by prioritising the safety and wellbeing of the client over the need to consent and collect data for the study. In some cases, this may mean that it may not be appropriate under very distressing circumstances to collect all of the client's study data.

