To ensure we collect data about service use and acceptability, we will seek to collect basic demographic data and brief views on service acceptability when service-users access the service. The pharmacy staff will explain this is a trial service and invite the individual to offer their views. The data will be collected during the consultation. The consultation will take place in a private consultation area to ensure privacy. Potential participants will be informed that all data collected for the research is anonymised.

Consent (for Part A and Part B as appropriate) will be obtained at the time of contact. Clients will be provided with a Participant Information Sheet and Participant Consent Form. Because of the nature of the service, prior consent is not possible and there is a limited time frame for the initiation of the intervention being tested. We recognise that the usual 24 hour notice period will therefore not apply.

The pharmacy staff will go through the participant information sheet with the service user. They will be invited to take this away if they choose. Information sheets will be made available in the additional languages of Polish, Lithuanian, Hindi and Urdu.

It will be explained that offering study information is entirely voluntary and declining to provide this additional information will not affect the care they receive in any way. Pharmacy staff will check for understanding and provide the opportunity for potential participants to ask questions and withdraw their consent at any time.

In terms of data collection, all of the client data is collected in the consultation. We did not feel that contacting participants after the service to collect follow up data would be appropriate (risk of breach of confidentiality / potential to raise suspicions with abusive partners).

The study data collected will not be extensive. It will comprise of simple demographic data, brief views about acceptability, satisfaction and health status. We already have extensive PPIE input in the design of these procedures. We will further test these as part of Phase 1 (co-development) of the study where we anticipate there will be further refinement of the triage process, referral and data collection tools.

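### Progression criterion 25 is named for clients' willingness but scored only on how completely the follow-up item is recorded, so its traffic light cannot register refusal

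*Protocol*

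**What the plan says.** The client data section (Protocol, part E, a. Usage and referral data) states that the consultation will collect "an indication of whether (for a future trial) completing a questionnaire and having a follow-up contact would be acceptable or not".

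Appendix 1, row 25, is labelled "Willingness to be followed up", with the pharmacy data sheets as its source. Its cells read:

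- Green: "Staff able to complete at least 80% of the data for at least 80% of the clients"
- Amber: "Failure to record at least 50% of the data for at least 50% of the clients"
- Red: "Failure to record at least 30% of the data for at least 30% of the clients"

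The same three cells appear in rows 22 to 24, which cover reasons for using the service, opportunistic or planned access, and demographics.

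Row 35, "Feasibility of a future trial – Is a trial possible", lists criterion 25 among the criteria to be considered. A footnote to the table says that a criterion recorded as red will be reviewed by the study team and the future design adjusted.

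The ethics section on collecting data from service users explains why nobody is followed up in this study: "We did not feel that contacting participants after the service to collect follow up data would be appropriate". The reasons given are confidentiality and the risk of arousing an abusive partner's suspicion.

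**The concern.** A progression criterion should change colour when the thing it is named for goes badly. Willingness has a favourable and an unfavourable answer, and the unfavourable one bears on how a later trial could be designed. For demographics or type of access there is no unfavourable answer, so completeness is a sensible test there. Carried over to row 25, the same wording tests the pharmacy staff's record keeping and not the clients' position.

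Because no client is contacted after the consultation, this item is the only direct client evidence on follow-up that the study plans to gather. If the pre-set signal cannot turn amber or red on refusal, noticing a refusal problem depends on someone choosing to look behind a green light.

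**Working it through.** No figure in the plan needs reproducing. The check is a reading of the rule.

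**Inputs**

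- What the item records: "completing a questionnaire and having a follow-up contact would be acceptable or not" (part E, a. Usage and referral data). A client who says no has a complete entry.
- Cut-offs: 80%/80%, 50%/50% and 30%/30%, all on recording (Appendix 1, row 25).

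**Notation.** Let c be the share of clients with the item fully recorded, and w the share of recorded answers that say follow-up is acceptable. For simplicity each client's entry is either complete or absent. Then the row reads:

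- green if c ≥ 80%
- amber if c < 50%
- red if c < 30%

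w appears in none of these conditions.

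**Test cases**

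| Recorded (c) | Willing (w) | Row 25 |
|---|---|---|
| 100% | 100% | Green |
| 100% | 0% | Green |
| 80% | 0% | Green |
| Below 30% | 100% | Red |

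Universal refusal, fully recorded, is green. Universal willingness, poorly recorded, is red. The third line shows that up to 100% − 80% = 20% of clients can have no entry at all and the row is still green with every recorded answer a refusal.

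**Is willingness scored elsewhere?** No other row of Appendix 1 sets a level for the share of clients who would accept follow-up. Where the authors wanted to score the content of an answer, they did so:

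- Row 6 scores whether pharmacies agree to be randomised.
- Row 31 scores the share of customers with positive views.
- Row 33 scores the share of survey respondents aware of the service.

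Row 6 is the nearest parallel: willingness to accept a trial procedure, scored on the answer given.

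**What follows from the colour?** The only consequence stated is the footnote's review of red criteria. A row that is green at w = 0% does not trigger it.

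**The case against.** The strongest reply is that rows 18 to 25 form a block. They share a data source, are labelled by data item, and are scored on whether staff could capture the item. On that reading row 25 asks only whether the follow-up question can be recorded, and the fault is its label. This is a fair account of the likely intent, and it is why the fix keeps the completeness line under a clearer title. It does not supply the missing test: willingness is then scored nowhere.

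Second, no decision turns mechanically on the colour. Row 35 is a consideration by the research team and the CTU with no go/no-go rule, it asks open questions about future outcomes and health economic measures, and the answers themselves will be in the database. This stands, and it limits the consequence. A reader might infer that a false green would commit the team to a trial that cannot follow people up; the documents do not support that.

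Third, a reader might infer that the future trial's cost-utility analysis is bound to require follow-up. The economic section prefers an EQ-5D cost-utility approach, but it leaves the type of evaluation and the model structure to be determined, and the primary clinical outcome to be chosen after this study. The present primary outcome, a count of consultations, needs no client follow-up. That follow-up may be wanted is a reasonable inference, not a stated requirement.

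Fourth, some clients will have no entry: they may decline the supplementary data (Part B), or staff may omit it in distress or urgency. Missing entries lower completeness, so the green result at zero willingness depends on refusals being recorded for at least 80% of clients. This stands as a condition.

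**Conclusion.** The point holds as a modest defect in the progression rule. As written, row 25 responds to recording and not to willingness. Provided refusals are entered and recording reaches the 80%/80% level, it is green at any share of willing clients from 0% to 100%. No other row covers the gap, and the red-review footnote would not be triggered.

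No probability is attached. The Study Summary makes the number of service users an outcome of the study, and the protocol gives no level of willingness that would count as sufficient, so any such figure would rest on invented inputs. The finding does not imply that the willingness answers will be lost or ignored; it says only that the pre-set signal does not carry them.

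**What to change.** 1. Retitle the present row 25 as capture of the follow-up item, and leave its completeness cut-offs in place.
2. Add a line scored on the proportion of clients asked who say that a follow-up contact would be acceptable and, separately, that a questionnaire would be. Report each with a 95% CI, together with the number of clients not asked or with the answer missing, since those who skip Part B may differ from those who answer.
3. Have the sponsor set green, amber and red levels for the new line before data are seen. Row 31 should not be cited as their source: it concerns general customers' views, and its red cell is worded as 30% or more positive, which shares in its amber and green ranges also satisfy.
4. Add the new line to the list considered under row 35.

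The cost is one row retitled, one row added and one cross-reference, using an item already collected in the consultation. The downsides are that the sponsor must commit to a cut-off, and that the estimate may be imprecise if few clients use the service.
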